7. STUDY DESIGN

7.1. Study design

The study will be a repeat cross sectional sero-epidmiology study, with an embedded longitudinal study cohort.

The goals of this study are to:

- Provide blood +/- saliva samples from 2300 children and young adults, representative of multiple geographic regions across England to evaluate the concentrations of antibodies against vaccine preventable diseases ('Group 1'). These need to be equally distributed such that there will be 100 in each of 22 age groups (1 year cohorts from 0 to 20 years) and 200 participants in the young adult cohort from 21 to 24 years). To help ensure these are representative of the study region recruitment will be from postcodes designated by PHE.
- To provide additional blood +/- saliva samples to assess changes in the proportion of children/adolescents with antibodies against SARS-CoV-2 during the COVID-19 pandemic. This will be achieved by:
 - Recruitment of additional participants (Group 2 and 3) that will not be included in the final vaccine sero-epidemiology analysis.
 - Group 2 participants will be recruited at all 'Group 1' sites, and at least 2 additional sites, and will be equally distributed across 4 age bands (0 4, 5 to 9, 10 to 14 and 15 to 19 years)
 - Group 3 participants, recruited at a sub-set of sites depending on capacity and the demographic profile of the local population
 - Taking up to 3 repeat blood samples (i.e. a total of 4 blood samples) at a minimal interval of 2 months apart from a sub-set of participants at all sites who consent for this (longitudinal sampling cohort, maximum number of participants enrolled defined in the clinical study plan). Participants in this cohort will also have a saliva sample collected at each follow-on visit.

• Evaluate T cell responses to SARS-CoV-2 infection. Within the longitudinal cohort selected sites who are able to provide blood samples to CCVTM for same-day processing for separation of peripheral blood mononuclear cells (PBMCs) will provide samples from participants who fit into the following groups:

- Have had no exposure, and are seronegative to SARS-CoV-2 at V1
- Have had a household exposure, but are seronegative at V1
- Have had symptoms of COVID-19, but are seronegative at V1
- Are seropositive at V1

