7.2. Study Sites

The study sites will be:

- University of Oxford
- Sheffield Children's Hospital NHS trust
- Bradford Teaching Hospitals NHS Foundation Trust
- Leeds teaching Hospitals NHS trust
- University Hospitals Bristol NHS Foundation Trust
- University of Southampton NHS Foundation trust
- Royal Manchester Children's Hospital Manchester University NHS trust
- St George's University Hospitals NHS Trust
- University of Nottingham Health Service
- University Hospitals Plymouth NHS Trust
- The Newcastle Upon Tyne Hospitals NHS Foundation Trust
- Imperial College Healthcare NHS Trust
- West Suffolk NHS Foundation Trust

Note that the Sheffield, Leeds and Bradford sites are collectively considered the 'Yorkshire and Humber region' for purposes of recruitment numbers. Nottingham and Plymouth will not be recruiting to Group 1.

GP practices and Pharmacies located in the same regions as the participating sites can be added as Participant Identification Centres in order to facilitate with recruitment.

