9. PROTOCOL PROCEDURES

9.1. Recruitment Group 1

The recruitment plan below aims to recruit a representative sample of the region. Potential participants will be contacted by mailing out invitation letters with study information booklets to the parents/legal guardians of age appropriate children via the NHS England Databases, the Child Health Information Service or through the Clinical Research Network. There may also be other promotion such as website based advertising, social media, radio, printed publications, contacting families registered with a study site research database and poster advertisements. Potential participants can also be identified by the local study team through their visits for other research studies. Dissemination of the study information, including through GP practices and with health visitors may also be employed. The participant information will be available on websites if available and recruitment material can direct potential participants to this. Participants interested in taking part will contact sites to arrange visits. In the first stage recruitment will be capped (e.g. at 10 per age group per region) to allow for corrections if the initial sample is not representative of the region.

We are aiming to ensure that the sample is broadly representative of the region according to IMD (Index of multiple deprivation scores). Other details collected in the questionnaire such as ethnicity, community identity and FASiii are for later analysis.

We are mailing out using NHS England Databases with the expectation that 5-10% of those contacted will respond.

Recruitment plan

- 1. PHE will be generating a list of all postcodes in recruiting regions and determining the quintiles of IMD (index of multiple deprivation scores) within that region.
- 2. All sites to email us postcodes in their catchment areas (i.e. areas from which they can recruit). They will also indicate whether they are rural or urban areas. There is a recognition that there is no formal definition of these terms, and many post codes will be mixed, but this is an area where local knowledge could be applied.
- For each region (i.e. Bristol, Yorkshire and Humber, Southampton etc.) PHE will randomly select 5-7 postcode districts stratified to match the ratio of rural to urban postcode districts to the region's urban/rural population distribution. A postcode district is the first two letters and number e.g.

OX	3	7	LE
Area	District	Sector	Unit

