11.2. Sample Size Determination

11.2.1: Group 1

The sample size for Group 1 is determined based on the primary objectives as well as the secondary objective to have a store of sera for future testing of immunity.

Historically serosurveys such as those done as part of the European Sero-epidemiology Network (ESEN) have had target sample sizes per age band of interest of 100-200. Age bands of interest have usually been one year bands until adult ages. For the purpose of this calculation this is taken as one year age bands to age 21 then a single band for 22-24 year olds. For the secondary objective 100 per age band will allow the precision of estimates of seroprevalence to be as given in table 2.

Table 2: Precision of seroprevalence estimates

Prevalence	95% CI Observed around the estimate with 100 per age band (2300 total)
10%	4.9-17.6
20%	12.7-29.2
30%	21.2-40.0
40%	30.3-50.3
50%	39.8-60.2
60%	49.7-69.7
70%	60.0-78.8
80%	70.8-87.3
90%	82.4-95.1

Precision will be improved when combining age bands for specific questions or when assessing trends by age for other secondary objectives. For example for diphtheria age bands of interest could be divided into <4,4-8,9-13,14-24 and for Men C into 0-10,11-12,13-15,16-19,20-24.

Focussing on the primary objectives

Representativeness of participants sampled

Within a study site representativeness is assessed by comparison to local population demographics. Each study region will have up to approximately 383 individuals allocated into Group 1. Overall all 2300 samples will be available for analysis in Group 1. With these numbers the precision of estimates of characteristics in the population and differences that would be significant to population data are given in Table 3. So, for example, if a specific ethnic group was 20% of the survey sample then in a region this would have a 95% Cl of 16.1-24.4% and would allow a proportion in the population of <14.3% or >26.6% to be detectable as different.

We will also compare our sample demographics with the population demographics of the corresponding NHS region. This will increase the sample size in some regions are there are multiple sites within that region.

	Re	gion (N=383)	Over	all (N=2300)	
Prevalence of	95% confidence	Prevalence below, above	95% confidence	Prevalence below,	
characteristic	interval	this in population that	interval	above this in population	
in sample		would significantly differ		that would significantly	
		(80% power, 5%		differ (80% power, 5%	

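### Table 3 gives regional precision only at the ceiling of 383 (2300/6) although nine study regions share the 2300, and Sections 7.1 and 11.2.1 set different Group 1 age bands

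*Protocol*

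**What the plan says.** **Regional numbers.** Section 11.2.1 sets the regional size: "Each study region will have up to approximately 383 individuals allocated into Group 1". It adds: "Overall all 2300 samples will be available for analysis in Group 1". Table 3 has a column headed Region (N=383), and the text illustrates it with a group making up 20% of the sample: a regional 95% CI of 16.1-24.4%, with population proportions below 14.3% or above 26.6% detectable at 80% power. No smaller regional N is shown.

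Section 7.2 lists 13 sites. It says that the "Sheffield, Leeds and Bradford sites are collectively considered the 'Yorkshire and Humber region' for purposes of recruitment numbers" and that "Nottingham and Plymouth will not be recruiting to Group 1". Section 9.1 uses region in the same site-based sense: "For each region (i.e. Bristol, Yorkshire and Humber, Southampton etc.) PHE will randomly select 5-7 postcode districts". The NHS region is a separate comparison in Section 11.2.1: "We will also compare our sample demographics with the population demographics of the corresponding NHS region".

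**Age bands.** Section 7.1 asks for "100 in each of 22 age groups (1 year cohorts from 0 to 20 years) and 200 participants in the young adult cohort", the last being ages 21 to 24, with a total of 2300. Section 11.2.1 describes the bands differently: "this is taken as one year age bands to age 21 then a single band for 22-24 year olds", with 100 per band and the same total.

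**The concern.** A regional size of 383 uses up 2300 in six regions, and more than six recruit to Group 1. Section 11.1 makes the site-level comparison with local population data part of the primary analysis of representativeness. If the typical region is well below 383, Table 3 is too favourable. A regional comparison that finds no significant difference would then be read as stronger evidence of representativeness than the numbers allow.

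The age bands raise a smaller problem. The count in Section 7.1 does not add up to its own total, and the oldest ages carry two different targets. It is therefore unclear whether Table 2's precision, which assumes 100 per band, applies to age 21.

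**Working it through.** **Inputs.** Group 1 total 2300 and regional N 383 (Section 11.2.1, Table 3); site list, merger and exclusions (Section 7.2); 80% power, 5% significance and a population at least 10 times the sample (Table 3 heading).

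**1. Counting regions.** 13 sites − 2 not in Group 1 = 11. Three Yorkshire and Humber sites become one: 11 − 2 = 9. They are Oxford, Yorkshire and Humber, Bristol, Southampton, Manchester, St George's, Newcastle, Imperial and West Suffolk. Merging St George's and Imperial as London (an assumption) gives 8.

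- 2300/6 = 383.3; 2300/9 = 255.6; 2300/8 = 287.5.
- 9 × 383 = 3447, well over 2300.
- Six regions at 383 would take 2298 and leave 2 participants for the other three. Four at 383 would take 1532 and leave 768 for five regions, about 154 each.

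**2. Reproducing Table 3.** The confidence limits are Clopper-Pearson with x = pN: lower = Beta(0.025; x, N−x+1), upper = Beta(0.975; x+1, N−x). The detectable limits solve for q in a two-sample test with k = 10, d = |p−q| and p̄ = (p + kq)/(1+k):

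- n₀ = [1.96√(p̄(1−p̄)(1+1/k)) + 0.842√(p(1−p) + q(1−q)/k)]² / d²
- with continuity correction, N = (n₀/4)[1 + √(1 + 2(1+1/k)/(n₀d))]²

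This reproduces all six rows of Table 3 to 0.1 at both N=383 and N=2300. For p = 20% and N=383 it gives 16.1-24.4 and 14.3, 26.6. The table is therefore correct for its stated N, and the question is only which N represents a region.

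**3. Same method at the average N, equal shares assumed.** Each cell gives the 95% CI, then the lower and upper detectable limits (%).

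| Prevalence | Stated, N=383 | N=288 | N=256 |
|---|---|---|---|
| 5% | 3.0-7.7; 2.3, 9.1 | 2.8-8.2; 1.9, 9.9 | 2.7-8.4; 1.8, 10.3 |
| 10% | 7.2-13.5; 6.0, 15.3 | 6.8-14.1; 5.4, 16.2 | 6.6-14.3; 5.2, 16.6 |
| 15% | 11.6-19.0; 10.0, 21.0 | 11.1-19.7; 9.4, 22.0 | 10.9-20.0; 9.1, 22.5 |
| 20% | 16.1-24.4; 14.3, 26.6 | 15.5-25.1; 13.5, 27.7 | 15.3-25.4; 13.2, 28.2 |
| 25% | 20.7-29.7; 18.8, 32.0 | 20.1-30.4; 17.9, 33.1 | 19.8-30.8; 17.5, 33.7 |
| 30% | 25.5-34.9; 23.3, 37.3 | 24.8-35.7; 22.3, 38.5 | 24.5-36.0; 21.9, 39.0 |

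At 20% and N=256 the interval is 10.1 points wide against 8.3 stated: 10.1/8.3 = 1.22, or 22% wider. At N=288 it is 9.6/8.3 = 1.16.

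**4. Age bands.**

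- Section 7.1 as written: 22×100 + 200 = 2400.
- Section 7.1 by its own age range, 0 to 20, which is 21 cohorts: 21×100 + 200 = 2300.
- Section 11.2.1: 22 one-year bands (0-21) plus one band for 22-24 = 23×100 = 2300.

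Both workable schemes give 200 participants aged 21-24 and 2300 overall. They differ on whether age 21 has its own target of 100. If Section 7.1's 200 were spread evenly over four years of age (an assumption), age 21 would have 50, and its CI at 50% would be 35.5-64.5 instead of Table 2's 39.8-60.2.

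**The case against.** - **383 is worded as a ceiling.** An average of 256 does not contradict that sentence, so a reader who infers that the protocol promises 383 in every region goes too far. What remains is that Table 3 and the example show only this upper limit and present it as what a region would have.
- **256 is not a protocol figure.** It needs nine regions and equal shares, and neither is stated. Equal shares are uncertain: the amendment history shows sites joining in April and December 2020, allocation to Group 1 is managed dynamically, and the monthly detail is in a clinical study plan not shown here. Some regions may come near 383 and others fall below 256. This stands: 256 is an average to plan on, not the true regional size.
- **Section 11.3 analyses representativeness in everyone providing a sample.** If that includes Groups 2 and 3, regional numbers could exceed 256. However, the 383 sentence and Table 3 concern Group 1, so this limits the claim about the final analysis and does not rescue the table.
- **The 22 is a slip with no numerical effect.** It probably is one, and it would be wrong to infer that 2400 are wanted or that any table is miscalculated because of it. Equally, 22 is the correct number of one-year bands under Section 11.2.1, so the count cannot be corrected before a scheme is chosen.
- **Age 21 is hardly affected.** Section 11.2.1 frames its bands as being for the calculation, and its example groupings pool age 21 with neighbouring ages (14-24 for diphtheria, 20-24 for Men C). A firm claim of 50 samples at age 21 is not supported, because the protocol does not say how the 200 are spread.
- **The shifts are modest and come late.** The limits move by 1 to 2 points in the 20% row, reported intervals will use the numbers achieved, and this version dates from the end of recruitment. That argues for a simple restatement, not for leaving the figures as they are.

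**Conclusion.** The concern holds in limited form. Table 3 is computed correctly for N=383, but 383 cannot be the general regional size within 2300 when Section 7.2 leaves nine study regions, or eight with London merged. Any reasonably even split leaves most regions below it. That six regions were once assumed is inferred from 2300/6 and is not stated; the conclusion does not depend on it.

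On equal shares, the regional CI in the 20% row is about 22% wider than stated at N=256 (16% at N=288). The detectable limits move outwards by 1.1 and 1.6 points at N=256 (0.8 and 1.1 at N=288). This is a moderate overstatement of regional precision for a primary outcome.

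The age-band conflict between Sections 7.1 and 11.2.1 is real but small. It affects the stated count and any single-year estimate at age 21. The 2300 total, Table 4 and the overall column of Table 3 are unaffected.

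**What to change.** 1. Recompute Table 3's regional column and the 20% example at the average N of about 256, stating the equal-share assumption. Alternatively, show a range such as 256 to 383 with 383 labelled as the maximum. Keep larger N for NHS-region comparisons that pool sites.
2. Use one age scheme in Sections 7.1 and 11.2.1 and Table 2. Either take 21 one-year cohorts (0-20) plus 200 aged 21-24, and do not claim Table 2's 100-per-band precision for age 21 alone; or take 22 one-year cohorts (0-21) plus 100 aged 22-24.

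The cost is restated figures and a few words of text. No participants or procedures are added. The only drawback is that regional precision looks somewhat worse than it does now.

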6. OBJECTIVES AND OUTCOME MEASURES

	Objectives	Outcome Measures
Primary	 To evaluate the feasibility and added public health benefit of an England, population based sero - epidemiological programme in 0 to 24 year olds 	 Representativeness of participants sampled, in terms of the local population's ethnicity, community identity, migrant population and socioeconomic background Comparison with serological markers of immunity for vaccine preventable diseases as measured in an age matched cohort in current residual sera programme
Secondary	 To evaluate the effectiveness of recruitment methods employed To assess, in relevant age groups, antibody concentrations against infections and vaccine preventable diseases including, but not limited to diphtheria, group C meningococcus and novel coronavirus (COVID-19) 	 Recruitment rate per month, recruitment rates as percentage of potential participants contacted, cost per sample obtained disease specific correlates of protection/markers of immunity, e.g. : Anti-Diphtheria Toxoid IgG concentrations Capsular Group C meningococcal Serum bactericidal activity (SBA) titres Serum IgG to SARS-CoV-2 antigens, including spike protein and/or nucleocapsid (as measured by ELISA and/or neutralising assay)
	• To develop a store of sera from a representative section of 0 to 24 year olds available for future testing of immunity against other infectious diseases of relevance to UK immunisation schedule and public health.	• A collection of anonymised sera from participants with appropriate consent and known demographic details and immunisation history'
	 To determine the prevalence of SARS- CoV-2 infections in 0 – 24 year olds, and variation in prevalence in time, age, ethnicity and geography (cross- sectional sero-epidemiological study) 	 Serum IgG to SARS-CoV-2 antigens, including spike protein and/ or nucleocapsid (as measured by ELISA and/or neutralising assay)

	 To determine the kinetics of antibodies specific to SARS-CoV-2 following infection in a paediatric population (serial blood sampling in population sub-group) To determine relationship between serum and salivary antibodies against SARS-CoV-2 	 Serum IgG to SARS-CoV-2 antigens, including spike protein and/or nucleocapsid (as measured by ELISA and/or neutralising assay) Salivary IgG to SARS-CoV-2 antigens, including spike protein and/or nucleocapsid (as measured by ELISA)

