7.4. Sample Size

2800 to 3800 participants, to provide blood +/- saliva samples as per section 7.1. This will include up to 300 participants specifically recruited to enhance representation of participants from Black, Asian and Minority ethnic groups with at least 100 from the Black/ African/ Caribbean/Black British community.

Additional samples can be received from other ethically approved research projects with the appropriate contractual arrangements in place provided that the participants have consented for the use of their samples outside of the study.

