8.3. Exclusion Criteria

The participant may not enter the study if ANY of the following apply:

- Group 1 only If participants do not live in the postcode districts selected by PHE
- Group 3 only if participants are not from the BAME population
- Participants who have a member of their household already enrolled in the study where their ages are less than 5 years apart.
- Any significant disease or disorder which, in the opinion of the Investigator, may either put the participants at risk because of participation in the research study, or may influence the result of the research study, or the participant's ability to participate in the research study. Examples of disorders or diseases which would be excluded include
 - Medically diagnosed bleeding disorder
 - o Medically diagnosed platelet disorder
 - o Anticoagulant medication
 - Pregnancy

Temporary exclusion criteria

The participant may not enter the study if they or any member of their household is under temporary isolation measures for suspected SARS-CoV-2 infection.

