- For prospectively collected samples where vaccination history is known, in individuals aged 12 -24 years, the proportion of individuals within each age band that have serum bactericidal titres of ≥8 to group C meningococcal disease, and whether SBA titres are associated with adolescent Men ACWY or MCC vaccine or not having received vaccine. Trends by age and differences by vaccination status will be assessed by Chi-squared of Fisher's exact test as well as by using logistic regression. Comparisons by geometric mean titres will also be done by t-tests or Kruskal Wallis as appropriate and by plotting geometric means with 95% confidence intervals by age groups.
- Across the whole age range (0-24 years) a comparison of proportions protected with previous seroprevalence studies carried out in 2009 and 1996 for diphtheria and 1996-99, 2002-4, 2009 and 2014 for Men C. This will be done by using all the samples and calculating prevalence within individual age bands with 95% confidence intervals and inferring differences based on non-overlapping 95% CIs which is conservative to allow for multiple testing when assessing many age bands.
- For all participants, a repeat cross-sectional analysis of the geometric mean titres (with 95% CI) of antibodies against SARS-CoV-2, and proportion (with 95% CI) of participants with anti SARS-CoV-2 antibodies above a (yet to be determined) threshold of 'positivity' throughout the study period
- For participants providing multiple serum samples, analysis of the proportion of participants who were initially seronegative who subsequently developed antibodies against SARS -CoV-2
- For participants providing multiple serum samples, analysis of the kinetics of the rise and fall of antibodies against SARS -CoV-2
- Calculation of the sensitivity and specificity of salivary antibody testing compared to serum.

Exploratory analyses

- Whether ethnicity, household income or other factors collected on the questionnaire are associated with antibodies against diphtheria and / or Men C and/or SARS-CoV-2. This will be done by multivariable logistic regression.
- Comparisons between groups 1 and 2 will be performed as detailed in study statistical analysis plan in terms of:
 - representativeness of ethnicity, community identity, migrant population and socioeconomic background of local communities
 - immunological end-points

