20%	20 (12.2, 27.8)	10 (0.2, 19.8)		individuals invited, for
30%	30 (21.0, 39.0)	20 (9.3, 30.7)	10 (0.0, 21.9)	representativeness will be
40%	40 (30.4, 49.6)	30 (18.7, 41.3)	20 (7.6, 32.4)	all individuals providing a sample and for
50%	50 (40.2, 59.8)	40 (28.6, 51.4)	30 (17.4, 42.6)	seroprevalence will all
60%	60 (50.4, 69.6)	50 (38.7, 61.3)	40 (27.6, 52.4)	individuals providing a
70%	70 (61.0, 79.0)	60 (49.3, 70.7)	50 (38.1, 61.9)	sample for which a laboratory result is

Table 5: Precision of estimates of change in prevalence with 100 samples at two time points.

obtained.

11.4. Group 3

Following discussions with Public Health England the suggested sample size would be 300 participants, with at least 100 from the Black/African/Caribbean/Black British community. This is based on preliminary data suggesting rates of seropositivity in adult males identifying as BAME are double that of the white community, and in those identifying as Black/ African/ Caribbean/Black British are 3 fold higher. Based on these proportions, and an estimate of 4% seropositivity in the white community, the above numbers would provide 80% power to detect similar differences in the paediatric populations.

The Level of Statistical Significance 11.5.

5% and 95% confidence intervals will be reported. For comparison across individual age bands for seroprevalence differences will be inferred based on non-overlapping 95% confidence intervals.

11.6. Procedure for Accounting for Missing, Unused, and Spurious Data.

The reason for missing data (consent withdrawn or unable to obtain any laboratory results) will be indicated. Missing data will not be imputed.

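### Section 11.3 contradicts Section 11.2.1 on who is in the primary representativeness analysis; read literally, it admits the BAME-only Group 3 to the ethnicity comparison

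*Protocol*

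**What the plan says.** **Primary outcome (Section 6).** "Representativeness of participants sampled, in terms of the local population's ethnicity, community identity, migrant population and socioeconomic background". Ethnicity is the first characteristic named.

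**Analysis population (Section 11.3, printed beside Table 5).** For representativeness it is "all individuals providing a sample and for" seroprevalence the same set, limited to those with a laboratory result. No group is named or left out.

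**Sizing of that outcome (Section 11.2.1).** "Each study region will have up to approximately 383 individuals allocated into Group 1", and "Overall all 2300 samples will be available for analysis in Group 1". Table 3 is built on these two numbers.

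**Group 3.** Section 7.4 plans "up to 300 participants specifically recruited to enhance representation of participants from Black, Asian and Minority ethnic groups". The matching exclusion in Section 8.3 reads "Group 3 only if participants are not from the BAME population".

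**Adjustment (Section 11.1).** For representativeness, the only factor named for multivariable adjustment is the age distribution.

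**SARS-CoV-2 trend.** Section 11.1 plans this "For all participants, a repeat cross-sectional analysis of the geometric mean titres" and of the proportion seropositive. Section 11.2.2 sizes the change in prevalence on Groups 1 and 2 combined. The only over-sampling it corrects for is that of participants seropositive at their first visit.

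**Vaccine serology.** Section 7.1 keeps Groups 2 and 3 out of the final vaccine analysis.

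**The concern.** Feasibility of representative recruitment is the primary objective. A group admitted by an ethnicity rule tells us nothing about whether the recruitment method reaches ethnic groups in proportion, so it should not be part of that test. If Section 11.3 is followed as written, the error can go either way. A sample that is in fact representative would show too many BAME participants. A Group 1 method that under-recruits them could look sound because Group 3 fills the gap. Age adjustment removes neither effect.

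Section 11.3 also admits Group 2, including the sites that recruit only to Group 2 through general publicity, and sets no bar on samples supplied by other studies, which Section 7.4 allows.

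The SARS-CoV-2 trend has a milder form of the problem. Section 11.4 supposes BAME seropositivity twice the white rate, and three times for Black participants. Group 3 joined late, so ethnic mix changes with calendar time.

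**Working it through.** **1. The plan's own figures.** Exact (Clopper-Pearson) intervals, and detectable population prevalences at two-sided 5% and 80% power with a population ten times the sample, were compared with Table 3.
- N=2300: all intervals reproduce. Detectable limits reproduce from 15% to 30% and lie within 0.1 point at 5% and 10%. For a 20% characteristic: interval 18.4 to 21.7, limits 17.6 and 22.5.
- N=383: all figures agree within 0.2 point. For 20% the table gives 16.1 to 24.4, limits 14.3 and 26.6; the check gives 16.2 to 24.5, limits 14.5 and 26.4.

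Table 3 is therefore sound for the Group 1 sample it describes.

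**2. Inputs for the distortion.**
- Group 3: 300, all BAME (Sections 7.4 and 8.3).
- Other participants: N = 3500 (2300 in Group 1 plus up to 1200 in Group 2); N = 2300 if only Group 1 is counted.
- True BAME share p: not in the documents. Assumed 10, 20 and 30%.
- The other participants are assumed to mirror the population.

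**3. False departure.** Pooled share s = (pN + 300)/(N + 300). Test against p: z = (s − p)/√[p(1 − p)/(N + 300)].

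| p | N = 3500 | z | N = 2300 | z |
|---|---|---|---|---|
| 10% | (350+300)/3800 = 17.1% | 14.6 | (230+300)/2600 = 20.4% | 17.7 |
| 20% | (700+300)/3800 = 26.3% | 9.7 | (460+300)/2600 = 29.2% | 11.8 |
| 30% | (1050+300)/3800 = 35.5% | 7.4 | (690+300)/2600 = 38.1% | 9.0 |

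Within one region, adding an assumed 50 or 100 Group 3 participants to 383 turns 20% into (76.6+50)/433 = 29.2% or (76.6+100)/483 = 36.6%.

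**4. Hidden shortfall.** At an assumed p = 15%, the share x in Groups 1 and 2 that pools to exactly 15% solves (3500x + 300)/3800 = 0.15. So x = (570 − 300)/3500 = 7.7%, about half the true share.

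**5. SARS-CoV-2 trend.** Rates are those of Section 11.4: 4% white, 8% BAME. Assume 15% BAME outside Group 3 and 50 Group 3 samples in a month of 400. (The 400 is the monthly goal that Section 5 states for 2020.)
- Without Group 3: 4% + 0.15 × 4% = 4.6%.
- With Group 3: BAME share (0.15 × 350 + 50)/400 = 25.6%, so 4% + 0.256 × 4% = 5.0%.
- Shift: about +0.4 point. The 95% half-width is 1.96 × √(0.046 × 0.954/400), about 2.1 points.

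If BAME shares run from 10 to 30%, and Group 3 seropositivity from 8% to 9.33% (100 of the 300 at 12%), the shift is +0.3 to +0.5 point when Group 3 is 10% of a month's samples, +0.7 to +1.2 at 25%, and +1.4 to +2.5 at 50%. Appendix C, used here only for timing, dates the addition of Group 3 to December 2020, so any shift falls after that.

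**The case against.** The best defence is that Section 11.3 only states data availability (invited, gave a sample, has a result) and that groups are assigned elsewhere. Section 11.2.1 ties representativeness to Group 1, Section 11.2.2 ties the SARS-CoV-2 change to Groups 1 and 2, Section 11.4 gives Group 3 its own purpose, and Section 11.1 lists a separate exploratory comparison of Groups 1 and 2. This stands against one inference a reader might draw, that the plan deliberately builds a distorted primary analysis. The documents show an unreconciled contradiction. It does not remove the problem, because Section 11.3 is the section that defines populations and its plain reading is the harmful one.

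A second defence is that such detail belongs to the statistical analysis plan. That holds for weighting methods. It does not hold for a population that the protocol itself fixes, inconsistently with its own sizing.

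Three other stronger readings are tempting and unsupported:
- *The seroprevalence trend is seriously distorted.* At the plan's rates the monthly shift is well inside sampling error unless Group 3 dominates a month. The doubling comes from adult males, and Section 11.1 also plans a regression of SARS-CoV-2 antibodies on ethnicity.
- *Vaccine seroprevalence is affected.* Section 7.1 rules this out.
- *Table 3's 12.9 to 17.3 is a tolerance band that a pooled 21.7% breaches.* Those limits are population prevalences that differ detectably from a sample value of 15% at N=2300. They are not limits for a pooled sample of 3800, so the tests above compare the pooled share with p directly.

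Finally, the hidden shortfall concerns the overall comparison. Section 7.1 has Group 3 recruited at only some sites, so under-representation could still show in site-level comparisons elsewhere.

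**Conclusion.** The contradiction is real and bears on the primary outcome. Followed literally, Section 11.3 yields a wrong ethnicity result: with 300 Group 3 participants among 3800, true shares of 10, 20 and 30% read 17.1, 26.3 and 35.5%, and a real shortfall to about half of an assumed 15% could vanish. These sizes rest on assumed population shares, full recruitment of Group 3 and an otherwise representative sample. The direction does not depend on the share chosen.

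The trend point is secondary. The shift is upward, small at the plan's rates and confined to the period after Group 3 was added.

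**What to change.** Amend Section 11.3 to name the groups for each analysis.

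1. **Primary representativeness:** Group 1 participants who gave a sample, as sized in Section 11.2.1. Exclude Group 3 and externally supplied samples. Section 2 says Group 1 allocation is managed, possibly after the study, so that the group is representative on geography and IMD. A sensitivity analysis can therefore add participants recruited through Group 1 procedures and later re-allocated to Group 2. Making that wider set the primary population would go beyond reconciling Sections 11.3 and 11.2.1.
2. **SARS-CoV-2 time trend:** Groups 1 and 2, as in Section 11.2.2, with the wording of Section 11.1 aligned. Keep Group 3 for the ethnicity contrast, or include it in the trend only when weighted to the population's ethnic distribution.
3. **Vaccine serology:** Group 1, restating Section 7.1.

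The cost is wording; no new data are needed. Group 3 stops adding numbers to the headline estimates. For the pooled SARS-CoV-2 estimate, going from 3800 to 3500 participants widens an interval by a factor of √(3800/3500) = 1.04.
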